9. TREATMENT OF SUBJECTS

9.1. Description of Study Medication

DE-117 Ophthalmic Solution 0.002% is an aqueous solution containing DE-117.

Figure 2: DE-117 Structure

Investigational Product:

- DE-117 Ophthalmic Solution 0.002% contains 0.02 mg/mL DE-117

Active Control:

- Timolol Maleate Ophthalmic Solution 0.5% contains the active ingredient, timolol 5 mg/mL. See [Section 21.5](#).

9.2. Concomitant Medications or Therapies

Medication or therapy considered necessary for the subject's welfare may be given at the discretion of the Investigator. Subjects may continue participation in the study if the instituted medication or therapy will not interfere with the evaluation of the study medication. Whenever possible, medications should be administered in dosages that remain constant throughout the study. Any treatment other than the study medication during the study duration will be considered as a concomitant treatment. The information of concomitant treatment must be recorded in the subject's source documents and on the eCRF.

- Concomitant medication: name of medication, route of administration, treated eye(s) (if applicable), dose, frequency, indication, start date and stop date.
- Concomitant therapy: name of therapy, treated eye(s) (if applicable), indication, start date and stop date.

9.2.1. Prohibited Medications or Therapies

- All ocular medications other than sodium chloride/potassium chloride ophthalmic solution, cataract treatment agents (e.g., glutathione, pirenoxine), Vitamin B₁₂

formulation (e.g., cyanocobalamin), over-the-counter dry eye artificial tears/drops, and study medications during the study duration.

- If artificial sodium chloride/potassium chloride ophthalmic solution, cataract treatment agents, Vitamin B₁₂ formulation, over-the-counter dry eye artificial tears/drops are concomitantly used, there must be an interval of **at least 5 minutes** between use of these ocular medications and use of the study medication.
- All systemic medications for ocular hypotensive (e.g., oral or intravenous CAI, oral glycerol) during the study duration.
- Any ocular, periocular, inhaled, nasal or systemic corticosteroids including joint injection, etc. during the study duration.
- Lacrimal/punctal occlusion via plug (s) or cautery during the study duration.
- Initiate or modify any systemic or topical medication known to affect IOP (e.g., β -adrenergic antagonists, α -adrenergic agonists, calcium channel blockers, ACE inhibitors, and ARB) within the first 30 days prior to Visit 1 (Screening) and during the study duration.
- Contact lenses within 2-3 weeks prior to Visit 2 (Baseline, Day 1) until end of treatment in either eye for adult subjects or in the eye being considered for study treatment for pediatric subjects (2 weeks for soft contact lens wearers, and 3 weeks for rigid contact lens wearers).
- Any ocular surgery or ocular laser treatment within 180 days prior to Visit 1 (Screening) and throughout the study in either eye for adult subjects or in the eye being considered for study treatment for pediatric subjects.
- Participation in any other clinical trial involving an investigational product within 4 weeks prior to Visit 1 (Screening) and during the study.

The decision to administer a prohibited medication or therapy should be made with the safety of the subject as the primary consideration. Whenever possible, Medical Monitor should be notified before any prohibited medication or therapy is administered. There may be additional prohibited therapies not mentioned above. Medical Monitor should be contacted if the permissibility of a specific medication or therapy is in question.

9.3. Treatment Compliance

To obtain reliable efficacy and safety data, the following precautions will be taken to ensure compliance with the treatment regimen during the study:

- Subjects will receive verbal and written instructions for proper instillation of the study medication, the dosing regimen, and the conditions of the study medication storage.
- Subjects will be reminded at study visits to consistently dose at the same time of the day.
 - Twice daily at 08:00 and 20:00 [± 60 min] through Visit 2 to 5

- Once daily at 20:00 [± 60 min] through Visit 5 to 8 for adult subjects only
- Subjects will be reminded of the evening instillation of the study drug on the day before Visit 3 through Visit 8/Early Termination respectively.
- Subjects will be reminded that the morning instillation of the study drug at each visit through Visit 3 to 5 will be done at the clinic.
- For adult subjects, since subjects must have a diagnosis of OAG or OHT in both eyes, both eyes should be treated for the duration of the study, even if only one eye is eligible per IOP inclusion criteria.
For pediatric subjects, if only one eye has a diagnose of glaucoma or OHT, the fellow eye doesn't have to be treated by the study medications for the duration of the study.
- Subjects will be queried regarding compliance with the protocol's dosing regimen at Visit 3 through Visit 8/Early Termination.
- Subjects will be counseled on proper dosing procedures and dosing schedule if the subject's compliance is not 100%.
- A subject's dosing compliance for a specific period is determined by the total number of days that subject followed the proper dosing procedures and dosing schedule. Stoppage of study medication use, overdosing of study medication, incorrect time of study medication administration, will be noted as non-compliance. The subject's dosing compliance will be recorded in the subject's source documents at Visit 3 through Visit 8/Early Termination.
- Subjects may be discontinued from the study at the discretion of the Investigator if the subject cannot be brought into compliance.

9.4. Randomization and Masking

A stratified permuted-block randomization will be employed to randomize eligible subjects in a 1:1 ratio to either DE-117/Vehicle arm or Timolol Maleate arm. Two strata will be constructed based on age (adult: ≥ 18 years; pediatric: < 18 years).

The randomization schedule will be generated and implemented using central randomization via Interactive Response Technology (Medidata BALANCE). Each randomized subject will receive numbered study medication kits as assigned by BALANCE.

This is a double-masked study through Month 3. The subjects, Investigators, Examiners and Santen personnel involved in the conduct of the study will be masked to the study treatment. An authorized unmasked study staff member who is not the Investigator or Examiner at the investigative site will dispense and collect study medication(s) and will query about dosing compliance. Subjects will be instructed not to show the eye drop bottles or discuss the eye drop to either the Investigator or the Examiner or other study subjects. The active control treatment (Timolol Maleate) containers will be over-labeled and packaged in the same secondary package (e.g., cardboard carton) as the investigational treatment (DE-117). All subjects will receive a bottle labeled "morning" for the morning dose and a bottle labeled "evening" for the evening dose.

At the completion of the Visit 5 (Month 3) procedures, the adult subjects will be dispensed open-label DE-117 Ophthalmic Solution 0.002% and instructed to dose once daily in both eyes at 20:00 for the duration of the study.

In case of a medical emergency, the Principal Investigator may reveal the treatment information by unmasking through Medidata BALANCE to know which treatment the subject has received. The Principal Investigator (or his/her designee) should contact Santen, or Santen's designee, before taking this measure, if there is sufficient time. Santen, or Santen's designee, must be informed of all instances where the code is broken and of the reasons for such instances.

[figure not shown]
Additionally, the AE or SAE for which study treatment was unmasked should be reported to Santen Pharmacovigilance.

10. STUDY MEDICATION MATERIALS AND MANAGEMENT

10.1. Study Medication

[figure not shown]
10.1.1. Investigational Product

DE-117 Ophthalmic Solution contains 0.002% or 0.02 mg/mL DE-117. Each 2.5 mL bottle of DE-117 Ophthalmic Solution 0.002% contains 50 µg of DE-117.

10.1.2. Vehicle

The vehicle

10.1.3. Active Control

The active control used in this clinical study, Timolol Maleate Ophthalmic Solution 0.5%, is supplied as a sterile, isotonic, buffered aqueous solution.

Timolol Maleate Ophthalmic Solution 0.5% contains the active ingredient, timolol 5 mg/mL and the preservative BAK 0.01%. Other ingredients include monobasic and dibasic sodium phosphate and purified water. The pH is adjusted to 6.5 to 7.5 with sodium hydroxide. See [Section 21.5](#).

10.2. Study Medication Packaging and Labeling

DE-117 Ophthalmic Solution 0.002% and DE-117 vehicle ophthalmic solution will be supplied as

Timolol Maleate Ophthalmic Solution 0.5% will be supplied as a 5 mL solution in a 5 mL white low density polyethylene bottle.

Each eye drop bottle will be placed in a unit carton. Four eye drop bottles/unit cartons of study medication will be placed in one kit. The eye drop bottles, unit cartons, and the kit will be labeled with the protocol number, kit number, storage conditions, and dosing instructions.

Kits dispensed at Visit 2 and Visit 4 (double-masked portion) will contain two (2) “morning” eye drop bottles and two (2) “evening” eye drop bottles of study medication. Kits dispensed at Visit 5, Visit 6 and Visit 7 (open label portion) will contain four (4) bottles of DE-117 ophthalmic solution 0.002%.

An authorized unmasked study staff member, other than the Investigator or Examiner, will dispense and collect study medications. When collecting the study medications, the kit containing all the used and unused eye drop bottles will be sealed.

10.3. Study Medication Storage

All study medication will be provided by Santen and will be stored in an appropriate secure area at the investigational site.

Study medications should be stored under refrigeration at 2° to 8°C (36° to 46°F), protected from light and stored upright. During the refrigeration storage, the Investigator (or his/her designee) will verify and record that the temperature was maintained at 2° to 8°C (36° to 46°F) using temperature recorder at least once every seven days at the investigational site, until the last subject has exited the study at the site. In the event of a temperature excursion or any study medications damaged during storage, the Investigator (or his/her designee) will notify Santen (or designee) and will not dispense the study medications until obtaining authorization from Santen (or designee).

Subjects will be reminded to store all dispensed eye drop bottles under refrigeration, protected from light and kept in unit cartons in an upright position. Study medications should not be frozen.

10.4. Study Medication Preparation

The study medications will arrive at the site prepared for instillation.

10.5. Study Medication Administration

Each subjects will instill one drop of study medication in each eye at approximately 20:00 ($\pm 60\text{min}$) and 08:00 ($\pm 60\text{min}$) daily for 3 months. Following visit assessments at Visit 5 (Month 3), adult subjects will instill one drop of study medication in each eye at approximately 20:00 ($\pm 60\text{min}$) daily for 9 months.

10.6. Study Medication Accountability

The Principal Investigator is responsible for ensuring that an inventory is conducted upon receipt of the clinical supplies. The temperature chart recorder from the shipment will be deactivated, and the Investigator (or his/her designee) will verify that the temperature was maintained at 2° to 8°C (36° to 46°F) during transit. In the event of a temperature excursion or any study medications damaged during transit, the Investigator (or his/her designee) will notify Santen (or designee) and will not dispense the study medications until obtaining authorization from Santen (or designee). The receipt of clinical supplies form should be completed, signed, dated, and returned as directed. A copy must be maintained at the site for the Investigator’s records.

The Investigator (or his/her designee) will keep a current record of the inventory, storage conditions and dispensing of all study medications. This record will be made available to Santen (or designee) for the purpose of accounting for all clinical supplies. Any significant discrepancy and/or deficiency must be recorded with an explanation.

All supplies sent to the investigational site must be accounted for and in no case will study medications be used in any unauthorized situation. It is the responsibility of the Investigator to ensure that any used and unused supplies are available to Santen (or designee) for accountability purposes throughout the study.

10.7. Study Medication Handling and Disposal

The used study medication kits will be stored at room temperature and the unused study medication kits will be refrigerated until final study medication accountability has been completed by Santen (or designee). Following final study medication accountability and reconciliation by Santen (or designee), all used and unused study medication will be returned to the assigned central drug depot.

10.8. Study Supplies

Commercial urine pregnancy test kits and customized blood sample collection kits for the pharmacogenomics/genomics will be provided by Santen (or designee).

11. ASSESSMENT OF EFFICACY

11.1. Efficacy Parameter

The IOP (mmHg) measured in the study eye (identified at the baseline visit) is the efficacy measure for this study. The IOP at each scheduled time point (08:00, 10:00 and 16:00) will be evaluated at each post-baseline visit. Besides observed IOP measurements, change and percent change from baseline in IOP at each scheduled time point as well as the change and percent change from baseline in mean diurnal IOP will also be derived and evaluated.

12. ASSESSMENT OF SAFETY

12.1. Adverse Events and Serious Adverse Events

12.1.1. Definition of Adverse Events

An adverse event (AE) is any untoward medical occurrence in a clinical trial subject. An AE does not necessarily have a causal relationship with the study medication. For this study, the investigational products are DE-117, DE-117 vehicle and Timolol. Regardless of relationship to the study medication, an AE can be a clinically relevant unintended sign (including an abnormal laboratory finding), symptom, or disease.

Any significant change in a subject's condition from the time that written informed consent is obtained, regardless of causality, is to be considered an AE. A clinically significant worsening in severity, intensity, or frequency of a pre-existing condition may indicate an AE.

An elective surgical procedure scheduled or planned prior to study entry that does not require an overnight hospitalization is not considered an AE, and the underlying diagnosis for the procedure should be captured in the medical history as a pre-existing condition. The surgical procedure should also include the term "elective" in all reports. An elective or planned hospitalization must be reported as an SAE.

The lack of efficacy of the study medication for the condition being investigated is not considered an AE unless a clinically significant change is assessed by the Investigator.

12.1.1.1. Assessment of Adverse Events

Investigators will seek information on AEs at each subject contact. Subjects should be asked using a general, non-direct question if there has been any change in their general health. Direct questioning and examination should then be performed as appropriate.

Severity of the AE should be assessed according to the following criteria:

Mild: No interference with the subject's daily activities; no medical intervention/therapy required.

Moderate: Possible interference with the subject's daily activities; no or minimal medical intervention/therapy required.

Severe: Considerable interference with the subject's daily activities; medical intervention/therapy required.

Regardless of severity, some events may also meet regulatory serious criteria. Refer to definitions and reporting of serious adverse events (SAEs) in [Section 12.1.2](#).

An Investigator who is medically qualified must make the determination of relationship (related or not related) to the investigational product for each AE or SAE. When determining relationship to study medication, the Investigator will consider any investigational products that a subject could be exposed to in this clinical trial. The Investigator should decide whether there is a reasonable possibility that the study medication caused the event, taking into account the following: a) evidence b) science-based rationale c) medical and clinical judgment

d) mechanisms of action e) biologic plausibility f) confounding risk factors (i.e., medical history, concomitant medications) g) temporal relationship h) dechallenge/rechallenge and i) lack of alternative explanation.

- The event may be recorded as **Related** to investigational product if:
 - There is a plausible temporal relationship between the onset of the AE and administration of the study medication
 - The AE abates or resolves upon discontinuation of the study medication or dose reduction and, if applicable, reappears upon rechallenge
 - The AE cannot be readily explained by the subject's clinical state, intercurrent illness, or concomitant therapies
 - The AE follows a known pattern of response to the investigational product
- Reporting the event as **Not Related** to study medication may be considered if:
 - There is good evidence that the AE has an etiology other than the investigational product (e.g., pre-existing medical condition, underlying disease, intercurrent illness, or concomitant medication)
 - The AE has no plausible temporal relationship to administration of the investigational product (e.g., cancer diagnosed 2 days after first dose of study medication)

12.1.1.2. Reporting Adverse Events

AEs, whether spontaneously reported by the subject or noted by authorized study personnel, will be recorded in the subject's medical record and on the appropriate AE electronic case report form (eCRF). Each recorded AE will be described by its duration (represented in dates), affected eye(s) (if applicable), maximum severity of the AE, seriousness criteria, suspected relationship to the study medication, actions taken with the study medication and the study participation, outcome of the AE, and any other attributable causes of the AE.

Regardless of relationship to the clinical study, AEs that occur at any time after the subject has provided written informed consent until subject withdrawal or the scheduled exit visit, must be recorded. To improve the quality and precision of acquired AE data, Investigators should observe the following guidelines:

- Whenever possible, use recognized medical terms when recording. Do not use colloquialisms and/or abbreviations.
- If known, record the diagnosis (i.e., disease or syndrome) rather than component signs and symptoms and /or laboratory or test findings (e.g., record congestive heart failure rather than dyspnea, rales, and cyanosis, and enlarged heart on chest x-ray). However, other events that are considered unrelated to an encountered syndrome or disease should be recorded as individual AEs (e.g., if congestive heart failure and severe headache are observed at the same time and are clinically unrelated, each event should be recorded as an individual AE).

- If the diagnosis is not known, then record the leading component sign, symptom or test finding and describe the other clinically related findings in the narrative description of the case. A suspected diagnosis can be used and described as such (e.g., record suspected or probable myocardial infarction); this has to be updated in the clinical database once the diagnosis is confirmed.

AEs occurring secondary to other events (e.g., sequelae) should be identified by the primary cause. A primary AE, if clearly identifiable, generally represents the most accurate clinical term. If a primary AE is recorded, events occurring secondary to the primary event should be described in the narrative description of the case. For example:

The subject developed orthostatic hypotension and subsequently fainted and fell to the floor wherein she experienced a head trauma and neck pain.

The primary AE in this example is orthostatic hypotension. The fall, head trauma and neck pain should be described in the narrative description of the case.

- For intermittent events (e.g., intermittent headache), the event onset date should be recorded as the date the subject first started to experience the event and resolution date should reflect when the last occurrence resolved or stopped. Separate AEs for each event should not be recorded. For example, if a subject experienced headache on 14SEP2015 lasting for three hours, then subsequently experienced intermittent episodes of headache every day for approximately 3 hours until 21SEP2015, then the AE date of onset is 14SEP2015 and the resolution date is 21SEP2015.
- For intermittent events, record the maximum severity of the individual events. For example, if a subject complains of intermittent headaches for one week and the severity of each headache ranges from mild to moderate, then the severity would be moderate.
- For intermittent hospitalizations occurring for a primary AE (e.g., in a subject with multiple sclerosis, commonly known for its relapsing and remitting course, in some cases leading to multiple hospital confinements), the subsequent hospitalizations should be described in the narrative description of the case.
- If treatment was initiated, include the treatment and duration of the medication(s) in the eCRF.

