12.1.2. Serious Adverse Events

12.1.2.1. Assessment of Serious Adverse Events

An AE is considered serious if it fulfills one or more of the following criteria:

- Death (i.e., the AE caused or led to death).
- It was life threatening (i.e., immediately life-threatening).
- It required or prolonged inpatient hospitalization.
- It resulted in a persistent or significant disability/incapacity (i.e., the AE resulted in a substantial disruption of the subject's ability to carry out normal life functions).

- It resulted in a congenital anomaly/birth defect in the offspring of a study subject who was exposed to study therapy prior to conception or during pregnancy.
- It is a medically significant event(s), which may include “sight-threatening events,” that may not meet any of the above serious criteria but may jeopardize the subject or require medical or surgical intervention to prevent one of the outcomes listed above.

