12.1.2.2. Reporting Serious Adverse Events

The SAE eCRF must be completed with as much information as is available within 24 hours of knowledge of the event.

To improve the quality and precision of acquired SAE data, Investigators should observe the following guidelines:

- Death: Death is an outcome of an event. The event that resulted in the death should be recorded and reported as the SAE.
- Hospitalizations for Surgical or Diagnostic Procedures: The illness leading to the surgical or diagnostic procedure should be recorded as the SAE, not the procedure itself. The procedure should be captured in the case narrative as part of the action taken in response to the illness.

Depending on the nature and seriousness of the AE, Santen may request additional documentation, for example, copies of the ophthalmic and medical records as well as results of laboratory tests. If the subject was hospitalized, a copy of the discharge summary may be requested.

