## 4.4. Safety-Related Definitions

### 4.4.1. Adverse Event

Under Protocol 011709IN, an AE is defined as any untoward medical occurrence that occurs in a study subject, regardless of the causal relationship with the study treatment. An *on-study* AE can occur any time after the date of informed consent through the last study visit. An AE will be considered as *treatment-emergent* if the onset date of the AE occurred on or after the treatment start date till up to 2 days (twice the scheduled dosing interval) after treatment end date.

Treatment-emergent AEs (TEAEs) are a subset of on-study AEs. Both on-study and TEAEs will be collected, but only TEAEs will be tabulated.

The severity of each AE will be graded by the Clinical Investigator as Mild, Moderate, or Severe. AEs will also be rated by the Investigator as to their causality/relationship to the study drug.

Each AE will be classified into a system organ class (SOC) and coded to a preferred term (PT) using Medical Dictionary for Regulatory Activities (MedDRA), Version 21.1 published in 2018.

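### The AE guidance sends secondary events to the case narrative with no stated exception for a non-fatal sequela that is itself serious, so such an event can lack its own preferred-term row and SAE flag.

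*Protocol*

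**What the plan says.** Protocol 12.1.1.2 (Reporting Adverse Events) opens with a duty: every AE from consent until withdrawal or the exit visit must be recorded, whatever its relationship to the study. It then lists guidelines that investigators should observe to improve data quality. One of these says that sequelae are identified by their primary cause, and continues: "If a primary AE is recorded, events occurring secondary to the primary event should be described in the narrative description of the case". The example is a subject with orthostatic hypotension who faints, falls and is injured. The hypotension is the primary AE, and "The fall, head trauma and neck pain should be described in the narrative description of the case". The same section asks for individual records where co-occurring events are clinically unrelated.

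Protocol 12.1.2.1 defines seriousness. Its last criterion covers medically significant events that "may jeopardize the subject or require medical or surgical intervention to prevent one of the outcomes listed above". Protocol 12.1.2.2 requires the SAE form within 24 hours of knowledge of the event and gives two naming rules. For deaths, "The event that resulted in the death should be recorded and reported as the SAE". For hospitalizations for procedures, "The illness leading to the surgical or diagnostic procedure should be recorded as the SAE, not the procedure itself".

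On the analysis side, SAP 4.4.1 assigns each AE a system organ class and a preferred term. SAP 4.4.1.1 takes SAE status from a yes/no question on the AE form. SAP 9.1 tabulates AEs and SAEs by class and preferred term, counting a subject once per class and once per term.

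**The concern.** The safety objective is a comparison with Timolol, and readers will make it mainly from descriptive AE and SAE tables by preferred term. Those tables show what is on the AE form. If a serious injury or other serious consequence of an AE is described only in free text, the table shows the cause and not the harm: a reader sees orthostatic hypotension and has to find the head trauma in a narrative.

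The example is relevant to this trial. The comparator's package insert (Protocol Appendix E) lists hypotension, syncope and bradycardia among reported reactions, so an injury that follows such an event is a plausible sequence. That shows relevance only; it says nothing about how often it would happen.

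**Working it through.** No arithmetic applies. The check is whether any text in the protocol or the SAP secures a separate record for a non-fatal sequela that is serious in its own right.

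1. **The guidance itself.** Protocol 12.1.1.2 attaches no condition on seriousness to the sequela rule, and the example sets no limit on how bad the head trauma may be. The route to individual records in that section is for clinically unrelated events, which a sequela is not.

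2. **Whether it forbids a separate record.** It does not. It is worded as what should be done, and as what generally gives the most accurate term where a primary AE is clearly identifiable. Contrast the intermittent-event rule in the same section: "Separate AEs for each event should not be recorded". The sequela rule has no such ban, but it does not ask for a record either.

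3. **The general duties.** Protocol 12.1.1.2 says that AEs must be recorded, and Protocol 12.1.2.2 says that the SAE form must be completed. A life-threatening or disabling sequela meets both definitions, so a careful site could well enter it separately. But the sequela guidance follows the recording duty as an instruction on how to record, and the SAE duty does not say whether a serious sequela has its own form or is covered by the primary AE's form.

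4. **The two naming rules in Protocol 12.1.2.2.** They say what to call the event: the cause of death and not death, the illness and not the procedure. The first secures a record of a fatal sequela, which is why this point is limited to non-fatal ones. Neither mentions secondary events.

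5. **Events of special interest.** Protocol 12.1.3 requires every case of macular edema to be reported, and SAP 9.1 summarizes events of special interest by class and term. These lie outside this point.

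6. **The SAP.** Coding, the SAE flag and the tables all start from a recorded AE. No step codes or extracts events from narrative text.

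Take one case, orthostatic hypotension followed by a non-fatal head trauma that meets a seriousness criterion, and trace both ways in which a site could record it:

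| Output | Sequela in narrative only | Sequela recorded separately |
|---|---|---|
| Any-AE total | subject counted | subject counted |
| Any-SAE total | counted if the primary AE is flagged serious | counted |
| Preferred-term row for the head trauma | none | present |
| SAE flag on the head trauma | none | present |

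The first column follows the guidance as written, and no later analysis step recovers its missing entries.

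**The case against.** The strongest reply is that primary-cause recording is a deliberate convention with a stated purpose. It codes a causal chain once, under its cause, and avoids several rows for one clinical episode. Mandatory duties sit above it. Each AE record carries maximum severity and seriousness criteria, and some of those criteria are causal, so hypotension that leads to a disabling injury can itself be flagged serious. Key ocular harms are captured in other ways: macular edema by special reporting, and visual acuity, slit-lamp and fundus findings by scheduled examination. SAP 6 plans no statistical tests on safety measures. Sites also receive instructions on completing the forms (Protocol 16.1), which cannot be seen here.

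Much of this stands. The convention is reasonable for most sequelae, the subject is not lost from the any-AE total, and no decision rule depends on these tables. But a serious flag on the primary AE does not give the sequela a row, and site instructions that may or may not address this do not change what the protocol says.

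Four stronger readings are tempting and are not supported:

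- **That separate records are prohibited.** The wording is guidance, and the intermittent-event rule shows how the protocol words a ban.
- **That Protocol 12.1.1.2 and 12.1.2.2 contradict each other.** The rules in 12.1.2.2 settle what to name an event, which is a different question, and they were not written to cover every seriousness criterion.
- **That severe but non-serious sequelae need their own rows too.** The protocol defines a severe AE as one with "Severe: Considerable interference with the subject's daily activities; medical intervention/therapy required", and this can be met without any seriousness criterion. Separate rows for these would be a debatable change to a deliberate convention.
- **That the tables favour one arm.** The same guidance applies to both arms, and through Month 3 the investigators are masked.

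**Conclusion.** The point holds as a minor gap in the recording guidance, worth considering for amendment. A site that follows Protocol 12.1.1.2 as written can leave a non-fatal sequela that is serious under Protocol 12.1.2.1 without its own preferred term or SAE flag. The any-AE total is unaffected, and the any-SAE total is unaffected provided that the primary AE is flagged serious.

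No size can be given. The documents do not state how often secondary events occur or how often they would be serious, and they give no basis for a direction of bias. The effect is confined to the descriptive safety tables.

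The conclusion assumes that sites follow the written guidance and that no instruction outside these documents already requires separate entry of serious sequelae. If such an instruction exists, the change only brings the protocol into line with it.

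**What to change.** Add one sentence to Protocol 12.1.1.2 after the sequela guidance: a secondary event that itself meets any seriousness criterion in Section 12.1.2.1 is entered as a separate AE/SAE record and linked to the primary AE; other sequelae remain in the narrative. Extend the orthostatic hypotension example by a line saying that a head trauma meeting a seriousness criterion is recorded in this way.

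Sites already apply this threshold to every AE, so no new judgement is asked of them. The cost is a link between records on the form, a few more AE and SAE records, and slightly higher event counts. Subjects are still counted once per class and once per preferred term under SAP 9.1, and the primary-cause convention is kept for all other sequelae. The SAP tables need no change.
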